4.1 Inclusion Criteria

- \geq grade 2 oral mucositis related to chemotherapy for cancer
- Ability to understand and the willingness to review and sign a written informed consent document.
- \geq 18 years of age
- Willingness to use adequate contraception prior to study entry, for the duration of study participation and for 30 days after the last dose for women of child-bearing potential and men

4.2 Exclusion Criteria

- Current use of therapeutic doses of anticoagulants such as warfarin or antiplatelet agents (prophylactic doses and agents are acceptable)
- Biliary tract obstruction or cholelithiasis
- History of gastric or duodenal ulcers or hyperacidity syndromes
- AST or ALT $>$ 2 x ULN
- Total bilirubin \geq 2 x ULN
- INR $>$ 1.5
- Previous stem cell transplant (allogeneic or autologous)
- Preexisting oral disease, such as active oral infection, trauma to the oral mucosa or oral ulceration prior to chemotherapy
- Known allergy/hypersensitivity to curcumin, yellow food colorings, or other members of the Zingiberaceae (ginger) family
- Pregnant or breastfeeding

Potential subjects are identified by medical record review. Eligible subjects are asked to give their written consent to participate in this study. The tests required to screen subjects for this study include a pregnancy test, INR and CMP.

5. Study Procedures and Schedule

The study mouth rinse will be initiated when subjects have $>$ grade 2 mucositis, which could be at any point during their chemotherapy cycle. Subjects who develop $>$ grade 2 mucositis will receive appropriate adjustments in their chemotherapy dose to reduce toxicity with subsequent cycles.

In the first part, there will be 3 subjects at each dose level of curcumin. Each dose will be given as a mouth rinse containing curcumin and water.

In the second part, subjects will be randomized to take a mouth rinse with the MTD of curcumin or a standard mouth rinse, 3 times each day for 14 days. The curcumin mouth rinse will be designated “study mouth rinse” to differentiate it from the standard mouth rinse.

All subjects will be instructed to rinse their mouths with the study or standard mouth rinse 3 times each day for 14 days. Subjects will be instructed to use the study or standard mouth rinse for 30 seconds and then swallow the rinse. Subjects will be instructed not to eat within one hour after using the study or standard mouth rinse. Subjects will be instructed to use a saline mouth rinse after eating any food to keep their mouth clean. A daily log (Appendix A) will be available for each subject and will include a checklist that will simplify the rinsing schedule as well as an area for the subject (or family member) to document mouth rinse administration. No other adjunctive topical treatment will be used during the study.

Subject adherence to the treatment schedule will be assessed through subject reports, by review of the daily log (Appendix A) and by review of returned medications collected during the site visits.

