Oral mucositis refers to erythematous and ulcerative lesions of the oral mucosa observed in patients with cancer being treated with chemotherapy, and/or with radiation therapy to fields involving the oral cavity. Oral and/or GI mucositis has been reported in 51% of patients receiving chemotherapy for solid tumors or lymphoma[1]. Clinically significant oral mucositis has been reported in an even higher percentage (approximately 75–80%) of patients who receive high-dose chemotherapy prior to hematopoietic cell transplantation[2]. Lesions of oral mucositis are often very painful and compromise nutrition and oral hygiene as well as increase risk for local and systemic infection. In addition to reducing patients' quality of life, mucositis may act as a dose-limiting adverse event in chemotherapy and/or radiation therapy and thus, it requires attention and treatment in the oncologic setting[3].

The cause of oral mucositis induced by cancer treatment is believed to be due to the over-production of free radicals induced by the chemo- or radiotherapy, which damages cell DNA and further activates pro-inflammatory transcriptional factors such as NF- κ B. Activation of NF- κ B up-regulates inflammatory cytokines. The major inflammatory cytokines involved are IL-6, TNF- α and IL-1 β [4, 5].

Typically, patients undergoing chemotherapy for cancer begin to show symptoms of oral mucositis about four to five days after starting treatment. Symptoms are at their peak at around the tenth day, after which they slowly improve over the following few weeks. Patients undergoing radiotherapy generally develop symptoms at the end of the second week of treatment. The symptoms can last from six to eight weeks.

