Potential subjects will be identified and recruited from within the practice population of the investigators (including via referrals to the investigators from other physicians). Patients' medical charts may be reviewed to identify potential subjects and to help determine eligibility; a 502-A form is being submitted to allow this preparatory to research activity.

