5.1.1 Visit 1 (Screening)

Subjects will be asked to sign a consent form. An oral exam will be conducted to ensure good oral hygiene. A blood or urine sample will be collected for pregnancy testing, if applicable. A blood sample will be collected to assess liver function (CMP) and clotting function (PT and INR). A mucositis assessment (CTAE version 4.0 and WHO Oral Toxicity Scale) will be conducted and documented by a health provider (Appendix B). This visit will take approximately one hour.

5.1.2 Visit 2

5.1.3 THIS VISIT MUST OCCUR WITHIN 48 HOURS AFTER THE SCREENING VISIT. IF VISIT 2 OCCURS ON A DIFFERENT DAY THAN VISIT 1, ANOTHER MUCOSITIS ASSESSMENT (CTAE VERSION 4.0 AND WHO ORAL TOXICITY SCALE) WILL BE CONDUCTED AND DOCUMENTED BY A HEALTH PROVIDER (APPENDIX B) AND WILL BE CONSIDERED THE BASELINE ASSESSMENT. THE PROVIDER WILL ALSO ASK THE SUBJECT TO COMPLETE A SUBJECT SELF-ASSESSMENT (APPENDIX C). SUFFICIENT MOUTH RINSE WILL BE GIVEN TO THE SUBJECT FOR THE FIRST WEEK OF THE STUDY. THE DAILY LOG (APPENDIX A) AND THE PATIENT SELF-ASSESSMENT TOOL (APPENDIX C) WILL BE GIVEN TO THE SUBJECT. THE SUBJECT WILL BE ASKED TO COMPLETE THE LOG EVERY DAY UNTIL VISIT 3. THE SUBJECT WILL BE ASKED TO COMPLETE THE SELF-ASSESSMENT TOOL ON DAY 3 OR 4 AFTER THE FIRST DAY OF TAKING THE MOUTH RINSE. A BLOOD AND SALIVA SAMPLE WILL BE OBTAINED FOR RESEARCH PURPOSES (SECTION 10). THIS VISIT WILL TAKE APPROXIMATELY 30 MINUTES.Phone call 1

On day 3 or 4 after the first day of taking the mouth rinse for the study, the subject will be called by a study staff member, who will review and follow up on any side-effects that the subject is experiencing and answer any questions about the study or study mouth rinse. The staff member will remind the subject to complete a subject self-assessment tool (Appendix C) and the daily log (Appendix A) and bring them to the next visit. The phone call will take about 15 minutes.

5.1.4 Visit 3

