5.6 Determination of MTD

The MTD will be determined as follows: If a DLT occurs in any one of the 3 patients at a specific dose level, an additional 3 patients must be treated at that dose level to achieve statistical validity of the MTD. If 2 of the 6 patients (17%) at a dose level develop a DLT, the previous dose level will be used as the MTD. If no DLT is observed, then the MTD will be the highest dose. To ensure safety of subjects at each dose level, all assessments will be completed at Visit 5 for subjects at a dose level before another subject is given study drug at the

subsequent dose level.

6. Expected Adverse Events

Toxicities will be graded by health care providers using the Common Terminology Criteria for Adverse Events (CTCAE) Version 4.0 weekly after initiation of study mouth rinse until mucositis is resolved (Grade 0) (see Provider Assessment in calendar, section 5.2). Toxicities will be assessed by subject self-evaluation during study mouth rinse administration between clinic visits (see Subject Assessment in calendar, section 5.2).

Very few studies have reported any severe or serious side effects from curcumin and most studies have involved oral administration of curcumin. No major toxicity has been found in studies where curcumin is used short-term. Increased bleeding may occur due to inhibition of platelet aggregation (very rare). Possible other side effects associated with curcumin include: vomiting, nausea, rash and GI distress. In a study of subjects with colon cancer, oral curcumin at doses ranging from 0.45 to 3.6 gram/day for 1 to 4 months was associated with nausea and diarrhea and caused an increase in serum alkaline phosphatase and lactate dehydrogenase[15]. In one study of patients with advanced pancreatic cancer, 5 of the 17 patients receiving oral curcumin (8 gram/day) in combination with gemcitabine reported intractable abdominal pain after a few days to 2 weeks of curcumin intake[16]. In a recent study of topical curcumin for mucositis in juveniles and children[14], there were no oral adverse events documented and no systemic adverse events that possibly could be related to the use of the curcumin mouthwash.

Patients will receive full supportive care as appropriate. The rationale for treatment, dosage and the date of treatment will be recorded in the medical record.

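### Section 6 names platelet inhibition as a way curcumin may increase bleeding, yet no screening test or exclusion concerns platelet count

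*Combined protocol and SAP*

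**What the plan says.** Section 6 (Expected Adverse Events) names a bleeding mechanism for the study drug: "Increased bleeding may occur due to inhibition of platelet aggregation (very rare". It also says that short-term use has shown no major toxicity.

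Two of the ten exclusions in Section 4.2 plainly address bleeding. One covers drugs: "Current use of therapeutic doses of anticoagulants such as warfarin or antiplatelet agents (prophylactic doses and agents are acceptable". The other is an INR above 1.5. On laboratory screening, Section 4.2 says: "The tests required to screen subjects for this study include a pregnancy test, INR and CMP". Section 5.1.1 describes the Visit 1 blood work: "A blood sample will be collected to assess liver function (CMP) and clotting function (PT and INR". The Section 5.2 calendar has rows for CMP and for PT/INR at screening and later visits. It has no row for a blood count at any visit.

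Section 4.1 requires mucositis of grade 2 or worse related to chemotherapy. Section 1 describes the condition: "Oral mucositis refers to erythematous and ulcerative lesions of the oral mucosa". Section 5 allows the rinse to begin when mucositis develops, "which could be at any point during their chemotherapy cycle". The rinse is swallowed after 30 seconds, at 1, 3, 6 or 9 g/day.

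**The concern.** The plan took bleeding seriously enough to exclude some patients and to measure PT and INR repeatedly. But the mechanism it names acts through platelets, and platelets are not examined. A patient whose platelet function is impaired by a therapeutic antiplatelet drug is kept out. A patient whose platelets are depleted by chemotherapy, which every subject has received, is not. The documents give no reason for treating the two differently.

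What is at stake is patient safety at entry. As written, the screening rule admits the patients with the least platelet reserve to a swallowed product that may inhibit platelets, while they have ulcerative oral lesions. There is also a smaller consequence for the dose finding. With 3 to 6 patients per level, each DLT matters, and a serious bleed in a patient with no recorded count would be hard to attribute to curcumin or to chemotherapy.

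**Working it through.** No figure in the plan bears on this point, so the check compares the sections.

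1. **Is a platelet count required?** Section 4.2 lists a pregnancy test, INR and CMP. Its wording could leave room for other tests, so two further places matter. Section 5.1.1 adds only PT. The Visit 1 column in Section 5.2 shows CMP and PT/INR and no blood count. All three agree. The research blood sample in Section 10.1 is for serum cytokines and is not used for eligibility.

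2. **Is there a platelet criterion?** Section 4.1 has 4 inclusion criteria and Section 4.2 has 10 exclusions, so 4 + 10 = 14 in all. Three exclusions carry a laboratory cut-off (AST/ALT, bilirubin, INR). None of the 14 concerns platelet count.

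3. **Does another item stand in for one?** PT and INR reflect the coagulation cascade, and a CMP is a chemistry panel, so neither shows a low platelet count. The drug exclusion acts on medication. The stem cell transplant exclusion removes some patients likely to have low counts, but not those on conventional chemotherapy. The exclusion for oral ulceration is confined to ulceration before chemotherapy, so it does not reach the lesions under study. Timing does not help, because the start is tied to no part of the cycle. Section 4 says "medical charts may be reviewed to identify potential subjects and to help determine eligibility", but a reviewer who sees a low count there has no criterion to apply.

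4. **When do the other protections act?**

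| Protection | Section | When it acts |
|---|---|---|
| All Visit 5 assessments finished at one level before the next opens | 5.6 | After the lower level has been dosed |
| DLT at grade 3 or worse, with removal of the subject | 6.1, 6.2 | After the event |
| Removal in the patient's best interest | 6.2 | After entry |
| Closure after two DLTs at the first dose; hold for any grade 5 toxicity | 6.3 | After the events |
| Side-effect phone calls, starting on day 3 or 4 | 5.1 | During dosing |
| Weekly review of toxicity trends | 12 | During dosing |

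None operates before a subject's entry on that subject's own platelet count. Staged escalation does protect later subjects. But a cleared level says little about thrombocytopenic patients unless some were treated there, and without counts nobody would know.

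5. **What would a count show?** Platelet reserve, not aggregation. It identifies the patients least able to tolerate the named hazard; it does not measure the hazard.

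6. **Size.** The documents support only this: 0 of 14 criteria and 0 required tests concern platelet count. They give no rate of thrombocytopenia or bleeding.

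**The case against.** The strongest reply is that the plan calls this bleeding very rare and has several layers of protection. Investigators are free to decline a patient whose count worries them. Section 6 also cites 17 pancreatic cancer patients who took curcumin at 8 g/day with gemcitabine. That is concurrent chemotherapy at 8/9 = 89% of the top dose, and the toxicity reported is abdominal pain in 5 of them, not bleeding. The drug exclusion accepts prophylactic agents, which suggests that some added bleeding tendency was considered and tolerated. Section 5.5 refers to the IND, which may hold a fuller safety basis. Finally, one count at screening leaves a treatment period of 14 days or more uncovered.

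Much of this stands. It keeps the point modest, and it is why the fix includes review of counts during treatment. It does not close the gap: the reassuring statements are not said to cover patients with low platelets, and freedom to decline a patient is not a criterion.

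A reader might infer more than the documents support:

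- **That subjects are unprotected.** They are not; the protections listed above are real, though they act after dosing.
- **That the danger lies at 9 g/day.** That level is 3 times the upper recommended dose (9/3) and slightly above the highest cited dose (9/8 = 1.125). Neither ratio measures bleeding risk, and the omission applies at every level.
- **That planned enrolment gives the number at risk.** The number of planned curcumin courses would be the same for any missing criterion.
- **That the ulcer exclusion is a third bleeding safeguard.** It reads "History of gastric or duodenal ulcers or hyperacidity syndromes". No rationale is given, and gastrointestinal irritation explains it equally well.

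**Conclusion.** The concern holds in this form: the plan names a platelet mechanism for bleeding, excludes on therapeutic antiplatelet or anticoagulant use and on INR, and has no test or criterion for platelet count. A severely thrombocytopenic patient with ulcerated mucosa is eligible at any dose level. The size of the risk cannot be estimated from the documents, and no number of bleeds is claimed.

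The conclusion rests on general knowledge of what PT, INR and CMP measure, and on the assumption that chemotherapy can lower platelets in this population. The protocol does not say the latter, although Section 11 collects duration of neutropenia and so anticipates low blood counts. The IND was not available and might lessen the concern. The change should be made before enrolment, because it is a cheap patient-safety measure. Confidence in its importance is medium.

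**What to change.** - Add a platelet count to the screening tests in Section 4.2 and to the Visit 1 column of Section 5.2. Apply footnote 4, so that it is not repeated if done for standard care, and state how recent such a result must be.
- Add an exclusion to Section 4.2 with a minimum platelet count fixed before enrolment. A natural default is to exclude a count that is CTCAE v4.0 grade 3 or worse, because the plan already uses that scale and treats grade 3 as dose-limiting. The investigators may choose a stricter value.
- Apply the criterion again to anyone who re-enters at a higher level or in Part 2, and before randomisation in Part 2.
- At each weekly visit, review any count available from standard care. Record the latest count with any bleeding event. A mandatory weekly count is not needed. If one is added, Section 6.1 should say that a platelet fall attributed to chemotherapy is not a curcumin DLT.

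The cost is low: one exclusion line, one data field and one count per screening, on blood already drawn at Visit 1. For enrolled courses that is 12 + 46 = 58 counts with no DLT, 12 + 3 + 46 = 61 under the stated total, or (4 × 6) + 46 = 70 if every level expands to six and escalation continues. Screen failures add to this, and counts already drawn for standard care reduce it. The downside is that a few candidates are excluded and enrolment may slow slightly; the documents do not allow that number to be estimated.

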This study will involve 12 subjects in the first part, plus an additional 3 subjects if a dose-limiting toxicity occurs (see section 2). This sample size is similar to other phase I dose escalation studies and will result in a determination of maximum-tolerated dose. The first objective for the second part (n=46) is to determine whether curcumin decreases an objective measurement of oral mucositis. Mucositis assessment will be conducted by the provider using the WHO scale and CTCAE scale. The scales are continuous between 0 and 4. Analysis of variance will be used to compare the two groups of subjects (standard mouth rinse versus study mouth rinse) separately for each time period (baseline and each week after study mouth rinse initiation). In a one-way ANOVA study, sample sizes of 23, and 23 are obtained from the 2 groups whose means are to be compared. The total sample of 46 subjects achieves 91% power to detect differences among the means versus the alternative of equal means using an F test with a 0.05 significance level. The size of the variation in the means is represented by their standard deviation which is 0.50. The common standard deviation within a group is assumed to be 1.00.

9. Measurement of Effect

Differences between the two mouth rinse groups will be studied with the chi-square test for categorical factors and the analysis of variance F-test for continuous variables with a 0.05 significance level.

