10.3 Future Research and Sample Disposition

Serum and saliva samples will be stored at -70°C in the Immunology Research Laboratory on the Aurora St. Luke's Medical Center campus. Samples will be coded. All patient identifiers will be removed. A key for the code will be stored in the office of the study staff. Only study staff will have access to the code. Samples that are left-over after the proinflammatory cytokine analysis will be stored at -70°C for future research on chemotherapy-induced mucositis. Subjects will be asked to complete a separate consent form for this future research. Samples will be stored until they are used up. If other researchers use the samples on an IRB-approved study, they will not be given any information that will link subject identifiers to the sample. If subjects do not consent to this future research, their leftover samples will be discarded following institutional procedures.

11. Data Collection

Data collected will include: patient demographic data, cancer treatment information (chemotherapy regimen, date started chemo), the name of the referring oncologist, dental work within the past six months and/or pre-existing mouth issues, medications within 30 days of screening, grade of oral mucositis prior to study and during the whole course of the study, pain scale, duration of mucositis, duration of neutropenia, the need and length of hospitalization, use and dosage of pain medicine, need for total potential nutrition, blood culture positive infection, other mucositis related complications and cytokine levels in blood and saliva.

If data from this study is published or otherwise shared with outside institutions, all identifying information will be removed and the data will be coded. The local study staff will have access to the code. There will be no differences in data collection between the different sites at Aurora Health Care that may eventually participate in this study.

12. Monitoring Plan

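### The rinse may start at any time in the chemotherapy cycle, but the arm comparison adjusts for neither time since chemotherapy nor baseline grade: a modest, avoidable loss of precision

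*Combined protocol and SAP*

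**What the plan says.** Section 5 (Study Procedures and Schedule) ties the start of the rinse to mucositis grade, "which could be at any point during their chemotherapy cycle". No start window is set, and no stratification factor is named for the 1:1 randomisation.

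Section 1 gives the expected course. Patients "begin to show symptoms of oral mucositis about four to five days after starting treatment". Then: "Symptoms are at their peak at around the tenth day, after which they slowly improve over the following few weeks".

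On analysis, section 8 says: "Analysis of variance will be used to compare the two groups of subjects", and does so "separately for each time period (baseline and each week after study mouth rinse initiation". The clock therefore starts at the first rinse and arm is the only factor. Section 9 repeats the rule in general form: "the analysis of variance F-test for continuous variables with a 0.05 significance level". Section 9.4 also counts healing time from the first rinse. No covariate appears anywhere.

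Two relevant baseline items are collected: the provider's baseline grade (section 9.1) and, in section 11, "cancer treatment information (chemotherapy regimen, date started chemo".

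**The concern.** On the plan's own account, two subjects with the same grade at first rinse can be at different points of the course, one still before the peak and one past it. Their remaining course without any treatment effect may differ, so part of the spread in weekly grade and in healing time may come from when the rinse began. A one-way ANOVA leaves that part in the error term.

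Two things follow. The interval for the arm difference is wider than it need be if the covariates matter. And in any one trial of 46 subjects, the arms can differ by chance in how far along natural recovery they are, which is the main competing explanation for apparent healing. Baseline grade and start day are known before treatment, so adjusting for them is legitimate if it is specified in advance.

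**Working it through.** **1. Reproduce the plan's figure.** Section 8 states: "In a one-way ANOVA study, sample sizes of 23, and 23 are obtained from the 2 groups whose means are to be compared". It gives a standard deviation of the means of 0.50, a within-group SD of 1.00, alpha 0.05 and power 91%. Two means each 0.50 from their average differ by 1.0 grade. The noncentrality is n × difference² / (2 × SD²) = 23 × 1.0² / 2 = 11.5. With 1 and 44 degrees of freedom, power is 0.912. The stated figure is right.

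**2. Is the unadjusted test valid?** Simulated trials with 23 per arm (20,000 per setting), with start day explaining 0 to 50% of the variance, gave a type I error of 0.047 to 0.051. There is no inflation.

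**3. Gain from adjustment.** The documents give no R² (share of variance in grade explained by the covariates), so 10-30% is an assumption. With total SD 1.00, the residual SD is √(1 − R²). One covariate degree of freedom is charged here.

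| R² | Residual SD | Interval narrower by | Power for 1 grade |
|---|---|---|---|
| 0 | 1.000 | 0% | 0.912 |
| 0.1 | 0.949 | 5% | 0.938 |
| 0.2 | 0.894 | 11% | 0.960 |
| 0.3 | 0.837 | 16% | 0.977 |

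Spending three degrees of freedom instead of one changes these powers by less than 0.001.

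**4. Fuller cost of three terms.** Degrees of freedom are not the whole cost, because covariate slopes must be estimated while the arms are not perfectly balanced on them. For p normally distributed covariates and N = 46, the average variance is multiplied by 1 + p/(N − p − 3). With p = 3 (baseline grade, and start day with a curved term) this is 1 + 3/40 = 1.075. Relative interval width is then √(1.075 × (1 − R²)):

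- R² 0: 1.037, about 4% wider
- R² 0.1: 0.984, about 2% narrower
- R² 0.3: 0.867, about 13% narrower

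Simulation (20,000 trials per setting) gave power of 0.891, 0.920, 0.946 and 0.967 at R² of 0, 0.1, 0.2 and 0.3. Break-even is R² = 1 − 1/1.075 = 7%.

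**5. Chance imbalance.** The spread of start days is not given. The standard error of the between-arm difference in mean start day is SD × √(2/23).

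| Assumed SD (days) | SE (days) | Chance of more than 2 days' difference |
|---|---|---|
| 3 | 0.88 | 0.024 |
| 4 | 1.18 | 0.090 |
| 5 | 1.47 | 0.175 |

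Suppose start day alone has R² of 10-30%, SD 4 days and a linear effect. The slope is √R² / 4 = 0.08 to 0.14 grade per day, so a 2-day imbalance moves the arm difference by 0.16 to 0.27 grade. The unadjusted standard error is √(2/23) = 0.295 grade. It already includes this source of error, so this is not a second loss on top of step 3.

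**6. If SD 1.00 does not include start-time spread.** The documents do not say. As an illustration, 0.10 grade per day with a start-day SD of 5 gives √(1 + 0.5²) = 1.118. Unadjusted power is then 0.843, and adjustment with one covariate restores 0.912.

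**7. A split at day 10.** For a normal covariate with a linear effect, splitting at the median keeps 2/π = 0.64 of R². The 10-30% becomes 6-19%, and power becomes about 0.93 to 0.96 on the basis of step 3.

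**The case against.** The strongest reply is that nothing is broken. Randomisation is concurrent and 1:1, the test keeps its level, and 91% is correct for the stated target. If SD 1.00 is the total SD, start-day spread is already inside that 91%. Efficacy is also a secondary objective; the primary one is the maximum tolerated dose. All of this stands, and it limits the point to efficiency.

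A second reply is that the rising-versus-falling contrast fades at the visits that matter. On the section 1 timeline, a subject starting on day 5 is at about day 12 at Visit 3 and day 19 at Visit 4. One starting on day 12 is at about days 19 and 26. Both are past the typical peak at every post-baseline clinic assessment. This also stands. Start day may still predict how far recovery has gone, but a reader who infers that it must be a strong predictor goes beyond the documents, which give neither an R² nor a spread of start days. The entry grade in section 4.1 narrows that spread further.

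Third, what start day contributes is only what it explains beyond baseline grade. That is why the gain above is stated for the covariates together.

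Finally, a reader might take the needed covariate to be already in hand. Section 11 lists a chemotherapy start date without saying which cycle it refers to. For a subject beyond the first cycle, it may not be the date needed.

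**Conclusion.** The point holds as a modest efficiency improvement. The plan allows an open start time, describes a time-dependent natural course, and then compares arms on arm alone.

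Under the assumption that baseline grade and start day together explain 10-30% of the variance in grade, intervals narrow by about 5-16% and power for 1 grade rises from 91% to about 94-98%. After the average cost of estimating three terms, the figures are about 2-13% and 92-97%. The degree-of-freedom cost is negligible; the fuller cost if the covariates explain nothing is about 2 points of power (0.912 to 0.891). The gain is positive once they explain more than about 7%.

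A reader might infer that the planned analysis is biased, that its error rate is inflated, or that the trial is underpowered for its target. The documents do not support any of these: arms are randomised concurrently and the power figure reproduces. That statement applies to the arms as randomised. Section 9.6 restricts the efficacy analysis to subjects who took at least 70% of doses, a selection made after randomisation, so balance in the analysed set is not guaranteed.

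**What to change.** For each post-baseline visit and each scale, replace the one-way ANOVA by a prespecified ANCOVA with:

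- arm;
- baseline grade on the same scale;
- days from the start of the current chemotherapy cycle to the first rinse, kept continuous, with one curved term (for example a quadratic) fixed in advance. A split at day 10 discards information, and the plan does not limit entry to one regimen or cycle length.

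Report the adjusted arm difference with its 95% interval as the main result and the unadjusted difference as supportive. Use the same covariates in the analysis of healing time. Add no further covariates: with 46 subjects, each one adds to the cost in step 4 of the working.

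In section 11, state that the chemotherapy start date is day 1 of the cycle under way at the first rinse.

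The cost is a paragraph of analysis text, one derived variable, up to three error degrees of freedom out of 44, and clarification of one date field. If that field now holds the first-cycle date, one extra date must be collected. No visit, dose or sample size changes.
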